### **2.7.3 Laboratory data**

Abnormalities according notable criteria (see [Appendix 2 of study protocol](#)) were identified. The proportions of patients with clinically notable abnormalities according to the notable criteria were summarized. Shift tables describing changes from status prior transplantation (Month 0) and Baseline based on the expanded normal limits were presented for treatment endpoints (study Month 6 and 18) and worst observations during the different study periods (up to Month 6 as well as between Month 6 and Month 18). The worst observation was defined as the highest or lowest measure during the different observations periods whereby

high or low were chosen according to the direction of abnormality (e.g. the highest will be chosen for serum creatinine, the lowest for leukocytes). Further, descriptive statistics of change from baseline of all laboratory variables were presented by visit. A by-patient listing of all laboratory data (with clinically notable abnormalities being flagged) was generated. Only assessments obtained up to 2 days after the discontinuation of study medication were considered “on-treatment” and analyzed with relationship to Everolimus.

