Abnormalities according notable criteria (see [Appendix 2](#)) will be identified. The proportions of patients with clinically notable abnormalities according to the notable criteria will be summarized. Shift tables describing changes from status prior transplantation (Month 0) and Baseline based on the expanded normal limits will be

presented for treatment endpoints (study Month 6 and 18) and worst observations during the different study periods (up to Month 6 as well as between Month 6 and Month 18). The worst observation is defined as the highest or lowest measure during the different observations periods whereby high or low are chosen according to the direction of abnormality (e.g. the highest will be chosen for serum creatinine, the lowest for leukocytes). Further, descriptive statistics of change from baseline of all laboratory variables will be presented by visit. A by-patient listing of all laboratory data (with clinically notable abnormalities being flagged) will be generated. Only assessments obtained up to 2 days after the discontinuation of study medication will be considered “on-treatment” and analyzed with relationship to Everolimus.

Vital signs

Vital signs variables include measurements of oral body temperature, systolic and diastolic blood pressures, pulse and body weight. Vital signs will be examined for abnormal values and change from Baseline according to pre-specified clinically notable criteria (see [Appendix 2](#)). Appropriate incidence rates of clinically notable abnormalities for between-group differences will be provided. Further, descriptive statistics of change from baseline of all vital signs variables will be presented by visit. A by-patient listing of all vital signs (with clinically notable abnormalities being flagged) will be generated. Shift tables describing changes from baseline based on clinically notable criteria will be presented for treatment endpoint (Month 18) and worst on-treatment observations. Only assessments obtained up to 2 days after the discontinuation of study medication will be considered “on-treatment”.

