Appendix 2: Clinically notable laboratory values and vital signs

Notable criteria		
Laboratory variable	Standard units	SI units
Liver function and related variables		
SGOT (AST)	$\geq 3 \times$ ULN	$\geq 3 \times$ ULN
SGPT (ALT)	$\geq 3 \times$ ULN	$\geq 3 \times$ ULN
GGT	$\geq 3 \times$ ULN	$\geq 3 \times$ ULN
Bilirubin	≥ 2.0 mg/dL	≥ 34.2 μ mol/L
Alkaline phosphatase	$\geq 3 \times$ ULN	$\geq 3 \times$ ULN
Albumin	None	None
Total protein	None	None
Renal function, metabolic and electrolyte variables		
Urea	None	None
Creatinine	>30% above baseline	>30% above baseline
Uric acid	M ≥ 12 mg/dL F ≥ 9 mg/dL	M ≥ 714 μ mol/L F ≥ 535 μ mol/L
Glucose	<45 mg/dL >250 mg/dL	<2.5 mmol/L >13.9 mmol/L
Cholesterol	≥ 350 mg/dL	≥ 9.1 mmol/L
Triglycerides	≥ 750 mg/dL	≥ 8.5 mmol/L
CPK (MB)	None	None
Sodium	None	None
Chloride	None	None
Potassium	≤ 3.0 mEq/L ≥ 6.0 mEq/L	≤ 3 mmol/L ≥ 6 mmol/L
Magnesium	<0.97 mg/dL >3.65 mg/dL	<0.4 mmol/L >1.5 mmol/L
Calcium	≤ 6 mg/dL ≥ 13 mg/dL	≤ 1.5 mmol/L ≥ 3.2 mmol/L
Phosphate	None	None
Amylase	$\geq 2 \times$ ULN	$\geq 2 \times$ ULN
Testosterone*	None	None
LH	None	None
FSH	None	None
Lipase	$\geq 2 \times$ ULN	$\geq 2 \times$ ULN

*male patients

Notable criteria		
Laboratory variable	Standard units	SI units
Hematology variables		
Hemoglobin	<7 g/dL	<4.39 mmol/L
Platelets (thrombocytes)	<50 k/mm ³ ≥700 k/mm ³	<50 × 10 ⁹ /L ≥700 × 10 ⁹ /L
Leukocytes (WBCs)	≤2.0 k/mm ³ ≥16 k/mm ³	≤2.0 × 10 ⁹ /L ≥16 × 10 ⁹ /L
Hematology variables: differential		
Granulocytes (poly, neutrophils)	≤1,000/mm ³	≤1 × 10 ⁹ /L
Eosinophils	≥12%	≥12%
Lymphocytes	≤1,000/mm ³	≤1 × 10 ⁹ /L
Urinalysis		
Albumin (mg/dL)	None	None
Glucose (mg/dL)	None	None
Erythrocytes	None	None
Protein/creatinine	<200 mg/g	<22.7 mg/mmol

Harmonized notable vital signs (and weight)

Vital sign variables	Notable criteria
Pulse (beats/min.)	None
Systolic BP (mm/Hg)	Either an increase of ≥30 that results in ≥180 or >200 (mm/Hg) or a decrease of ≥30 that results in ≤90 or <75 (mm/Hg)
Diastolic BP (mm/Hg)	Either an increase of ≥20 that results in ≥105 or >115 (mm/Hg) or a decrease of ≥20 that results in ≤50 or <40 (mm/Hg)
Temperature (°C)	None
Weight (kg)	None

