### **2.7.4.2 Vital signs**

Vital signs variables included measurements of oral body temperature, systolic and diastolic blood pressures, pulse and body weight. Vital signs were examined for abnormal values and change from Baseline according to pre-specified clinically notable criteria (see Appendix 2 of study protocol). Appropriate incidence rates of clinically notable abnormalities for between-group differences were provided. Further, descriptive statistics of change from baseline of all vital signs variables were presented by visit. A by-patient listing of all vital signs (with clinically notable abnormalities being flagged) was generated. Shift tables describing changes from baseline based on clinically notable criteria were presented for treatment endpoint (Month 18) and worst on-treatment observations. Only assessments obtained up to 2 days after the discontinuation of study medication were considered “on-treatment”.

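### The worst-value rule for laboratory shift tables names only the lowest value for leukocytes and has no provision for variables that are notable in both directions

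*SAP*

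**What the plan says.** SAP 2.7.3 plans laboratory shift tables for "treatment endpoints (study Month 6 and 18) and worst observations during the different study periods"; the two periods are up to Month 6 and Month 6 to Month 18. For the worst observation it takes the highest or the lowest measure in the period: "high or low were chosen according to the direction of abnormality (e.g. the highest will be chosen for serum creatinine, the lowest for leukocytes". Protocol 10.6.2 has the same rule ("The worst observation is defined as the highest or lowest measure during the different observations periods") and the same example for leukocytes ("the lowest for leukocytes").

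The shift tables are graded by expanded normal limits: "Shift tables describing changes from status prior transplantation (Month 0) and Baseline based on the expanded normal limits were presented for treatment endpoints". Neither document defines these limits.

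Two other outputs in SAP 2.7.3 do not pass through the worst-value rule. One is a summary by the Appendix 2 criteria: "The proportions of patients with clinically notable abnormalities according to the notable criteria were summarized". The other is a by-patient listing of all laboratory values with notable ones flagged.

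Nothing elsewhere in the SAP adds to the rule. Section 5.4, on laboratory derivations, only points back to Appendix 2, and section 4, on changes to the protocol analyses, does not mention it.

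**The concern.** A worst value in one direction suits a variable for which only one direction matters, such as creatinine. Appendix 2 shows that the sponsor regards both directions as relevant for four variables that protocol 7.6 lists as collected. If only one extreme is carried forward for these, the worst-observation table can show a patient as unchanged although a value on the other side was out of range.

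This matters because the remaining shift tables cover only Months 6 and 18. Table 7-1 schedules haematology and biochemistry also at Months 8, 9, 10 and 12, which include the switch phase. An abnormality confined to those visits can enter a shift table only as the worst observation.

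**Working it through.** The plan gives no figure to reproduce, so the check sets the rule beside the limits and applies it to short series.

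**Inputs.** Limits are from Protocol Appendix 2; directions are from SAP 2.7.3 and Protocol 10.6.2.

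| Variable | Notable low | Notable high | Direction named in the rule |
|---|---|---|---|
| Leukocytes (k/mm³) | ≤2.0 | ≥16 | lowest |
| Platelets (k/mm³) | <50 | ≥700 | none |
| Potassium (mEq/L) | ≤3.0 | ≥6.0 | none |
| Glucose (mg/dL) | <45 | >250 | none |

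Calcium and magnesium also have two limits in Appendix 2, but they are not on the protocol 7.6 laboratory list and are left out.

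**Logic.** Suppose the lowest value is taken and the patient has at least one value above the upper limit. There are three cases:

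- The lowest value is within limits: the patient is shown as normal and the high value is missed.
- The lowest value is below the lower limit: the patient is shown as low and the high value is missed.
- The lowest value is itself above the upper limit: the patient is still shown as high.

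Taking the highest value gives the mirror image.

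**Made-up series.** The Appendix 2 limits stand in for the expanded normal limits, which are not given.

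| Series in one period | Using the lowest | Using the highest |
|---|---|---|
| Leukocytes 6, 18, 7 | 6, not notable | 18, high |
| Leukocytes 17, 18, 19 | 17, high | 19, high |
| Platelets 250, 720, 300 | 250, not notable | 720, high |
| Potassium 4.5, 6.2, 4.4 | 4.4, not notable | 6.2, high |
| Potassium 2.8, 4.5, 6.2 | 2.8, low | 6.2, high |
| Glucose 100, 260, 110 | 100, not notable | 260, high |
| Glucose 40, 100, 260 | 40, low | 260, high |

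For leukocytes the rule names the lowest, so the first series loses its 18 and the second does not. For the other three variables the classification depends on a choice the plan leaves to the programmer. In the second potassium series and the second glucose series, either single choice drops a real abnormality.

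**What other outputs recover.** The leukocyte value of 18 is at or above 16, so it still counts in the notable proportion and is flagged in the listing. A leukocyte value above the expanded upper limit but below 16 is not notable. If it occurs at Month 8, 9, 10 or 12 and the patient's lowest value is within limits, no shift table or notable count shows it. It then appears only in the unflagged part of the listing and, averaged with other patients, in the by-visit change from baseline.

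**The case against.** The strongest reply has four parts.

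- **The direction could be read per patient.** On that reading the worst value is taken on whichever side the patient is abnormal, and nothing is dropped. For platelets, potassium and glucose the text does not exclude this. But both worked examples assign a direction by variable, and the per-patient reading gives no answer for potassium 2.8, 4.5, 6.2. What stands is that, outside leukocytes, the fault is an unspecified rule. A reader might infer that the plan fixes one direction for all four variables; it does not.
- **Notable values are caught elsewhere.** This is correct. The notable proportions and the flagged listing work in both directions, and under protocol 7.6 a laboratory abnormality that is clinically significant, symptomatic or needs therapy is also an adverse event. A reader might infer that these abnormalities vanish from the safety analysis, or from all shift tables. The documents do not support that: the Month 6 and Month 18 shifts use the values at those visits.
- **Low counts are the trial's concern.** The dose-adjustment text (protocol 6.5.2, 6.5.5 and Appendix 5) targets leukopenia, neutropenia and thrombocytopenia, so the lowest leukocyte value is a sensible choice if only one is shown. That explains the choice, but it does not settle potassium or glucose.
- **The tables are descriptive.** No test or endpoint depends on them. This stands and keeps the point small.

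Two further inferences go too far. One is that every patient abnormal only in the other direction is shown as normal; leukocytes 17, 18, 19 disprove it. The other is that the same rule governs blood pressure. SAP 2.7.4.2 refers to "worst on-treatment observations" but states no highest-or-lowest rule, and its tables use the clinically notable criteria, which cover both rises and falls in blood pressure. There, worst is simply undefined.

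**Conclusion.** The point holds as a minor improvement to the laboratory shift tables. It covers four variables and only the worst-observation tables. For leukocytes, the stated rule misses a high excursion whenever the lowest value in the period is within limits. For platelets, potassium and glucose, the plan does not determine the result, and any single direction can miss the other. The part that no other table makes good is mainly excursions between Month 6 and Month 18 that lie outside the expanded normal limits but short of notable.

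The conclusion assumes that the expanded normal limits have an upper and a lower bound for these variables and are tighter than Appendix 2. The documents do not show this. The number of patients affected cannot be derived, and no primary or secondary endpoint is touched.

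**What to change.** In SAP 2.7.3, state that for leukocytes, platelets, potassium and glucose both the lowest and the highest value per period are derived, and that shifts from baseline to lowest and from baseline to highest are both presented. Keep one direction for one-sided variables such as creatinine. In SAP 2.7.4.2, add a sentence saying how the worst blood-pressure observation is chosen. A definition of the expanded normal limits would let a reader interpret all of these tables.

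The cost is a short text edit and a few more descriptive tables from data already collected. One extra direction for 4 variables over 2 periods is 4 × 2 = 8 further shift panels for each reference status used.

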## **2.7.4 Other safety data**

### **2.7.4.1 ECG and cardiac imaging data**

Any clinically significant abnormalities were presented as past/current medical condition.

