9. Venous blood will be drawn for measurement of the C0-h levels of Cyclosporin A or Tacrolimus and Everolimus.
10. Venous blood will be drawn for frozen storage until end of trial (2 EDTA-tubes, **2-5 mL**).
11. In woman of childbearing potential a pregnancy test will be performed (β -HCG).
12. Urinalysis for proteinuria will be performed (spot urine sample for protein/creatinine ratio may be used).
13. Changes in Concomitant medications / significant non-drug therapies will be recorded.
14. (Changes in) immunosuppressive medication will be recorded.
15. Information on rejection episodes, hemodynamic compromise, MACE, hospitalization, infections, and other (S)AEs that occurred since the last visit will be recorded.

Switch of immunosuppressive regimen - Visit 3 (Month 8 post Tx)

This visit may be performed within a time window of \pm 1 week.

1. Vital signs will be measured.
2. Venous blood will be drawn for measurement of hematology and biochemistry.
3. In woman of childbearing potential a pregnancy test will be performed (β -HCG).
4. Venous blood will be drawn for measurement of viral serology (CMV status including pp65 Ag)
5. Venous blood will be drawn for measurement of
 - Everolimus C0-h level in all patients
 - Cyclosporin A C0-h level, only in patients of the CNI group

- Tacrolimus C0-h level, only in patients of the CNI group
- 6. Changes in concomitant medications / significant non-drug therapies will be recorded.
- 7. Changes in immunosuppressive medication (including study drug dosage) will be recorded.
- 8. Information on rejection episodes, hemodynamic compromise, MACE, hospitalization, infections, and other (S)AEs that occurred since the last visit will be recorded.

Maintenance Period - Visits 4, 5 and 6 (Month 9, 10, 12 post Tx)

These visits may be performed within a time window of \pm 1 week.

- 1. Vital signs will be measured.
- 2. An endomyocardial biopsy will be performed (only visits 4 and 6).
- 3. A 12-lead ECG will be written (not at month 10, Visit 5).
- 4. Venous blood will be drawn for measurement of hematology and biochemistry.
- 5. Venous blood will be drawn for the measurement of viral serology (only CMV-status including pp65 Ag).
- 6. Venous blood will be drawn for measurement of
 - Everolimus C0-h level in all patients
 - Cyclosporin A C0-h level, only in patients of the CNI group
 - Tacrolimus C0-h level, only in patients of the CNI group

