- 7. In woman of childbearing potential a pregnancy test will be performed (β -HCG).
- 8. Changes in concomitant medications / significant non-drug therapies will be recorded.
- 9. Changes in immunosuppressive medication (including study drug dosage) will be recorded.
- 10. Information on rejection episodes, hemodynamic compromise, MACE, hospitalization, infections, and other (S)AEs that occurred since the last visit will be recorded.

Only at Visit 4, Month 9

- 11. A complete physical examination will be performed.
- 12. Venous blood will be drawn for frozen storage until end of trial (2 EDTA-tubes, **2-5 mL**).
- 13. Urinalysis for proteinuria will be performed (spot urine sample for protein/creatinine ratio may be used).

End of Study - Visit 7 (Month 18 and early discontinuation)

In case of early discontinuation, Month 18 assessments need to be performed

- as soon as possible after study drug discontinuation
- additionally at the originally planned timepoint, i.e. 18 months after transplantation

1. A complete physical examination will be performed.
2. Vital signs will be measured.
3. An endomyocardial biopsy will be performed.
4. A 12-lead ECG will be written.
5. Venous blood will be drawn for measurement of hematology and biochemistry.
6. In woman of childbearing potential a pregnancy test will be performed (β -HCG).
7. Venous blood will be drawn for measurement of viral serology (CMV-status including pp65 Ag).
8. Venous blood will be drawn for measurement of
 - Everolimus C0-h level in all patients
 - Cyclosporin A C0-h level, only in patients of the CNI group
 - Tacrolimus C0-h level, only in patients of the CNI group
9. Venous blood will be drawn for frozen storage until end of trial (2 EDTA-tubes).
10. Urinalysis for proteinuria will be performed (spot urine sample for protein/creatinine ratio may be used).
11. Changes in concomitant medications / significant non-drug therapies will be recorded (in case of early discontinuation until 30 days after last dose of study drug).
12. Changes in immunosuppressive medication (including study drug dosage) will be recorded (in case of early discontinuation until 30 days after last dose of study drug).
13. Information on rejection episodes, hemodynamic compromise, MACE, hospitalization, infections, and other (S)AEs that occurred since the last visit will be recorded
14. End of Study / End of Treatment information will be obtained.

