The allograft will be presumed to be lost on the day the patient is scheduled for re-transplantation. This will be reported on the End of Treatment CRF if medication is discontinued prematurely and Study Completion CRF. Graft loss / re-transplantation are considered a Serious Adverse Event and must be reported on the Serious Adverse Event Case Report Form, which must be faxed to Novartis.

Major Adverse Cardiac Events (MACE)

Major Adverse Cardiac Event will be defined as one of the following:

- any death
- myocardial infarction
- coronary artery bypass grafting

All major adverse cardiac events will be recorded on the CRF and are subject to expedited reporting as specified in [section 8.1](#).

- **Echocardiogram**

Echocardiograms will be performed as needed for suspected rejection episodes. Results will be recorded on the Echocardiogram CRF.

- **Electrocardiograms (ECG)**

A 12-lead ECG will be written and documented in the CRF with ventricular rate, PQ interval, QRS duration and QT interval.

Additionally, the investigator will assess the following:

heart rate: normal, bradycard, tachycard,
rhythm: eurhythmia, arrhythmia,
block signs: S-A Block,
 AV-Block °I, °II (Wenckebach, Mobitz, Periodic), or °III,
 Interventricular Block (right bundle-branch, left bundle-branch)

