## **2.2.1 Subgroup of interest**

## **2.3 Patient disposition, demographics and other baseline characteristics**

Demographic and background information was summarized for the ENR-, the SAF- and the FAS - Population, using frequency distributions for categorical variables and descriptive statistics of mean, standard deviation, minimum, median and maximum for continuous variables. Background information included prior medication, past/current medical conditions and transplant history.

Medical history was coded using MedDRA and was presented by system organ class, MedDRA preferred term and treatment group. Separate tables were provided for past medical condition and current medical condition. Prior medication was coded according to WHO Drug Reference List.

In addition to these variables which were evaluated at Screening (Visit 1, Month 3 post Tx), the course of renal function (GFR) as well as efficacy variables (treated acute rejection, biopsy proven acute rejection of ISHLT 1990 grade  $\geq 3A$  resp. ISHLT 2004 grade  $\geq 2R$ , acute rejection associated with hemodynamic compromise, graft loss / re-transplantation, death) were determined and properly described for the run-in period between Screening (Visit 1, Month 3 post Tx) and Baseline (Visits 2, Month 6 post Tx).

The two treatment groups were compared descriptively with respect to these variables.

No formal statistical testing was conducted for comparability purposes.

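### SAP 2.7.4.1 sets no time limit on filing ECG and imaging abnormalities as medical conditions, and no by-arm summary of the post-randomization ECGs is planned

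*SAP*

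**What the plan says.** SAP 2.7.4.1, under other safety data, consists of one sentence: "Any clinically significant abnormalities were presented as past/current medical condition".

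SAP 2.3 says where such conditions are reported. "Background information included prior medication, past/current medical conditions and transplant history", and "Medical history was coded using MedDRA and was presented by system organ class, MedDRA preferred term and treatment group". The next paragraph places these items in time: "In addition to these variables which were evaluated at Screening (Visit 1, Month 3 post Tx". It ends: "The two treatment groups were compared descriptively with respect to these variables".

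Protocol 7.5 says what is collected: "A 12-lead ECG will be written and documented in the CRF with ventricular rate, PQ interval, QRS duration and QT interval". The investigator also rates heart rate, rhythm and block signs. The visit descriptions in Protocol section 7 require an ECG at Visits 1 and 2, at Visits 4 and 6 ("A 12-lead ECG will be written (not at month 10, Visit 5"), and at Visit 7 ("A 12-lead ECG will be written").

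The protocol synopsis lists ECG and echocardiogram among the efficacy assessments. Its data analysis paragraph commits to descriptive statistics and between-treatment comparisons for every safety and efficacy variable other than the primary one.

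**The concern.** The rule covers any clinically significant abnormality and has no cut-off date, but its destination is a background table. A conduction or rhythm finding that first appears at Month 9, 12 or 18 is an outcome under treatment, not history. In a background table split by arm, it would look like a baseline imbalance.

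Separately, rate, PQ, QRS, QT, rhythm and block data are recorded on the CRF three times after randomization, and the SAP gives them no table. In heart transplant recipients under two different immunosuppressive regimens, a shift in conduction or rhythm that no site judged significant in a single patient would leave no trace in the planned output.

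**Working it through.** No effect size or power figure is involved. The check is a count and a trace through the documents.

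**1. How many recordings are affected.** ECGs are scheduled at Visits 1, 2, 4, 6 and 7, that is Months 3, 6, 9, 12 and 18 (Protocol Table 7-1 and the visit descriptions). Randomization is at Month 6, so 3 of the 5 follow it. SAP 1.1 gives 162 randomized patients: 3 × 162 = 486. This assumes that every patient attends every visit and counts Visits 7 and 7.1 as one time point. It counts recordings, not abnormalities.

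**2. Where a new clinically significant finding goes.** Take a block first seen at Month 12.
- SAP 2.7.4.1 sends it to medical conditions, which are background items in SAP 2.3.
- Protocol 7.6 makes an abnormal test result an adverse event if it is considered clinically significant, and says that AEs may be detected through assessments at visits. SAP 2.7.1 analyses treatment-emergent AEs of the randomized period by randomized arm.

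The two documents use the same trigger, clinical significance, and point to different tables. For physical examination, Protocol 7.6 makes the split that is missing here: findings present before enrollment go to medical history, and later findings that meet the AE definition go to the AE form.

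**3. What happens to the measurements.**

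| Data | Change from baseline by visit | Shift table | Notable criteria |
|---|---|---|---|
| Laboratory (SAP 2.7.3) | yes | yes | yes |
| Vital signs (SAP 2.7.4.2) | yes | yes | blood pressure only |
| ECG (SAP 2.7.4.1) | none | none | none in Protocol Appendix 2 |

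**4. Whether the omission is declared.** SAP section 4 lists two changes: the imputation of missing primary data and the handling of non-randomized patients. ECG is not mentioned. SAP 2.12 says there are no additional exploratory analyses, so the tables are not planned there either.

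**5. What other routes still capture.**
- AEs are analysed by arm (SAP 2.7.1).
- Rejection with hemodynamic compromise, defined in Protocol 6.5.3 by ejection fraction, fractional shortening and/or inotrope treatment, is a component of treatment failure. Each component is compared by log-rank test (SAP 2.6.2).
- Myocardial infarction and bypass grafting are compared the same way within MACE.
- Pulse is summarized with the vital signs.

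Two things remain uncovered: ECG intervals, rhythm and block ratings not individually reported as AEs, and echocardiographic findings short of hemodynamic compromise. For the latter the AE route is weaker, because echocardiograms are done for suspected rejection, and Protocol 7.5 keeps rejection episodes off the AE form.

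**The case against.** The strongest reply is that the ECG sentence was meant for findings present at entry. SAP 2.3 ties medical conditions to Screening, and the protocol's rule for physical examination shows the intended split. On that reading a new significant finding is an AE by protocol definition, not by site choice, and is already tabulated by arm. In addition, ECG is not among the key safety variables in Protocol 10.6.2 or the secondary efficacy variables in 10.6.1, and the protocol's detailed analysis sections never promise interval or shift tables.

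Much of this stands. A reader might infer that ECG abnormalities are never compared between arms, or that the planned output cannot show any cardiac difference. The documents do not support either. The AE tables, hemodynamic compromise and MACE are all compared by arm, and even the medical-condition tables are split by treatment group and compared descriptively. Nor does the SAP say that the rule applies to every visit; it names none.

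What does not stand is that nothing needs to change. If the sentence is for Screening only, post-randomization ECGs have no rule at all. If it is not, it contradicts the AE definition. Either way the data from Months 9, 12 and 18 lack the description and comparison that the synopsis promises. That commitment is general, but ECG is named among the assessments in the same synopsis.

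**Conclusion.** The point holds in a limited form. SAP 2.7.4.1 has no time limit and, read literally, conflicts with the protocol's AE definition. No by-arm summary of the post-randomization ECG data is planned, and section 4 does not declare this.

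The size is up to 3 scheduled ECGs per patient, at most about 486 in all. A reader might take 486 as the number of findings lost. It is not: the documents give no abnormality rate, and clinically significant findings reported as AEs are still compared. The conclusion rests on a literal reading of one sentence and on the absence of any other ECG analysis in the SAP. The primary analysis, sample size and power are unaffected.

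**What to change.** 1. In SAP 2.7.4.1, limit the medical-condition rule to findings present before study treatment or randomization.
2. State that later clinically significant ECG or imaging findings are reported in the treatment-emergent AE tables by randomized arm, in line with the AE definition and the physical examination rule in Protocol 7.6.
3. Add a descriptive summary by visit and arm of ventricular rate, PQ, QRS and QT, and a shift table from Month 6 to Months 9, 12 and 18 for rhythm and block findings. If these tables are not wanted, declare and justify the omission in SAP section 4.

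The cost is a few sentences and a few descriptive tables from data already on the CRF. No test or multiplicity adjustment is needed.
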